13.1.3.2 Supportive analysis of primary and key secondary endpoints

The following analyses will be performed in the FAS, FAS without exacerbation during double-blind treatment and VCS.

- Descriptive: absolute and change variables (change from V2 to V6)
- ANCOVA on change variables (from V2 to V6) with covariates as in the primary analysis plus stratification factor as covariate. Point estimates of adjusted treatment differences will be presented with confidence intervals.

- Poisson regression with covariates as in the primary analysis without confirmatory testing (i.e. p-values associated with treatment effect are interpreted along exploratory lines). Point estimates of adjusted treatment ratios will be presented with confidence intervals.
- Descriptive: absolute and change variables (change from V2 to V6) in subgroups formed by COPD stage, smoking status, concomitant LABA use and former ICS use (4 subgroup analyses).
- Poisson regressions with covariates as in the primary analysis plus covariates indicating COPD stage, smoking status, concomitant LABA use and former ICS use (4 different models) without confirmatory testing. Point estimates of adjusted treatment ratios with confidence intervals will be presented

13.1.3.3 Analysis of secondary endpoints

These analyses will be performed in the FAS (but the key secondary variable CD68+ cell count will be analysed as described above). They will be descriptive by treatment and visit (all visits from V1 or V2 to V5 or V6 with data available, pulmonary function data include V0), by ANCOVA on absolute change from baseline (V1 or V2 depending on parameter) to last available measurement during double-blind treatment (for Subjects with complete data V5 or V6 depending on parameter) for continuous variables (covariates: baseline value, treatment, stratification factor) or Poisson regression with dispersion parameter for count data at visit with last measurement on double-blind treatment (completers: V5 or V6; covariates: baseline count, treatment, stratification factor). In Poisson regression models the area investigated will be included as an offset variable in the model.

- **Cell count in biopsied material (sub-mucosa) [cells/mm²]:**
 - 1) CD68+ descriptive, Poisson regression (key secondary endpoint): see Sections [13.1.3.1](#) and [13.1.3.2](#)
 - 2) Neutrophils: descriptive, Poisson regression
 - 3) CD4+: descriptive, Poisson regression
 - 4) CD45+: descriptive, Poisson regression
- **Cell count in biopsied material (bronchial epithelium) [cells/mm²]:**
 - 1) CD8+: descriptive, Poisson regression
 - 2) CD68+: descriptive, Poisson regression
- **Total and differential cell counts in induced sputum absolute [cells/mL]:**
 - 1) Neutrophils: descriptive, ANCOVA
 - 2) Macrophages: descriptive, ANCOVA
 - 3) Eosinophils: descriptive, ANCOVA

- 4) Lymphocytes: descriptive, ANCOVA
- **percentage [%]:**
 - 1) Neutrophils: descriptive, ANCOVA
 - 2) Macrophages: descriptive, ANCOVA
 - 3) Eosinophils: descriptive, ANCOVA
 - 4) Lymphocytes : descriptive, ANCOVA
- **Concentration of inflammatory biomarkers in sputum:**
 - 1) Inflammatory mediators: descriptive, ANCOVA
- **Concentration of inflammatory biomarkers in blood serum:**
 - 2) Inflammatory mediators: descriptive, ANCOVA
- **Metabolomics**

The data from the measurement of a panel of different metabolites in blood serum will be analysed in exploratory terms. The metabolomics analyses will be described in a separate statistical analysis plan. Results will go into a separate report. These analyses will not be part of the main SAP or main CSR.
- **Pulmonary function changes in the course of the trial:**

Change from randomization (V2) over 16 weeks of treatment for:

 - 1) FEV₁ [L], FVC [L], FEV₁/FVC [%]: descriptive

13.1.4 Other Analyses

Health economic evaluations are not planned.

The analysis for the following exploratory objectives will be described in a separate statistical analysis plan and the results will go into a separate report. These analyses will not be part of the main SAP or main CSR.

- **Microbiome:** The interaction between changes in the lung microbiota, airway inflammation and mucin production resulting from roflumilast therapy ([Appendix I](#))
- **Transcriptome:** To study the molecular anti-inflammatory treatment effects of Roflumilast in study RO-2455-402-RD ([Appendix J](#))
- **Airway Reflux:** An exploratory research approach to study the changes of the degree of airway reflux ([Appendix K](#))

13.1.5 Safety Analysis

The safety analyses will be performed in the SAF.

13.1.5.1 Adverse Events

Incidences of AEs will be summarized by MedDRA preferred term (PT) and system organ class (SOC). Such summaries will be provided for all baseline AEs, all treatment-emergent AEs, treatment-emergent AEs leading to death, treatment-emergent AEs leading to withdrawal, treatment-emergent non-serious AEs, treatment-emergent serious AEs, treatment-emergent serious AEs leading to withdrawal, treatment-emergent AEs judged to be related (Investigator) to the trial treatment or to trial procedures, treatment-emergent serious AEs judged to be related (Investigator, Investigator and/or Sponsor) to the trial treatment, and treatment-emergent AEs judged to be related to the trial treatment and leading to withdrawal. In addition treatment-emergent AEs (SOC and PTs) will be summarised also by intensity, association to the trial treatment, outcome, time to onset and duration. Preferred terms by descending frequencies will be provided for all treatment-emergent AEs, treatment-emergent AEs judged to be related to the trial treatment, treatment-emergent serious AEs, and treatment-emergent AEs leading to withdrawal.

Further details regarding the analysis of AEs will be given in the SAP.

13.1.5.2 Clinical laboratory evaluations, ECGs, vital signs

Clinical laboratory data will be presented on an individual basis and will be marked according to the normal ranges provided by the selected central laboratory. Descriptive summary statistics, including changes from randomization (V2), will be presented for each variable. In addition, the number of values outside the normal ranges and outside extended ranges will be presented.

The data from ECG and vital signs will be presented in a descriptive manner as well.

13.1.5.3 Body weight and BMI

Weight change [kg] and BMI change [kg/m^2] will be analysed using an ANCOVA model including LOCF. The dependent variable will be the change from randomization (V2) to the last scheduled post-randomization visit up to visit V6. The following factors and covariates (all fixed) will be included in the model: treatment and baseline value.

In addition, pre-treatment with LABA (yes/no) will be included in the model as this is used as stratification factor in the randomization (CPMP/EWP/2863/99) [25].

Descriptive summary statistics (N, mean, SD, median, 68% range, minimum and maximum) will be provided for all scheduled visits (absolute values as well as changes from baseline) by treatment. A Subject data listing by treatment and visit will be provided showing body weight [kg] and BMI [kg/m^2] (absolute values as well as changes from baseline).

Further details regarding body weight and BMI will be given in the SAP.

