The results of the two pivotal studies were confirmed and extended by two six-months studies (trials BY217/M2-127 and BY217/M2-128) evaluating the effect of Roflumilast as add-on treatment to long-acting bronchodilators [8]. In these studies, pre-bronchodilator FEV₁ (primary endpoint in both studies) was significantly improved by 49 mL beyond the bronchodilator effect of concomitant treatment with salmeterol in trial BY217/M2-127 and by 80 mL incremental to concomitant treatment with tiotropium in trial BY217/M2-128. Although not designed to show treatment effects on exacerbations, both studies suggested beneficial effects of Roflumilast in this respect.

Further two 1-year trials (M2-111 and M2-112) similar to the pivotal studies but using a different patient population also showed significant effects of Roflumilast in terms of lung function and indicated beneficial effects in terms of exacerbations. These studies also indicated that the effects of Roflumilast are independent of ICS (which was prohibited in the pivotal studies).

In all studies performed, Roflumilast was generally safe and well tolerated under long-term exposure (once daily administration for up to one year). Diarrhoea, weight decreased, nausea, abdominal pain and headache, were the most frequently reported AEs and considered associated with intake of Roflumilast. With respect to the event of weight decrease, weight measurements in the two pivotal studies showed a larger mean weight loss in Roflumilast-treated patients compared to placebo-treated patients which was however reversible upon Roflumilast withdrawal [9]. Roflumilast was also associated with an increased risk of psychiatric disorders such as insomnia, anxiety, nervousness and depression. Rare instances of suicidal ideation and behaviour, including completed suicide, have been observed in clinical trials. A causal relationship to Roflumilast could neither be established nor excluded due to the low number of cases and the known increased risk of COPD patients for depression and suicides.

Roflumilast (DAXAS[®]) was approved in the European Union by the European Commission on 5 July 2010 for the maintenance treatment of severe COPD (FEV₁ post-bronchodilator less than 50% predicted) associated with chronic bronchitis in adult patients with a history of frequent exacerbations as add on to bronchodilator treatment.

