9.1.4 Weight, Height

Body weight measurements will be performed at each visit from V0 to V7. Measurements should be done to the nearest 0.1 kg after emptying the bladder and with Subjects standing barefoot and wearing light indoor clothing.

Body height will be measured at visit V0 during the run-in period in bare feet, standing Subjects.

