13.3 Determination of Sample Size

Based on the extensive literature search/review and experimental data provided by the Steering Committee (SC) members the team concludes that significant differences exist between reports published by various groups, which may be attributable to different patient populations, bronchoscopy/tissue harvesting/processing methods and statistical methods employed (see attached table below).

Additionally based on SC members' opinion a universally recognized level of clinical relevance regarding the first primary variable (sub-mucosa CD8+ cells) has not yet been agreed upon within the scientific community of chest physicians and pathologists. But it has been indicated by SC members that a 30% improvement on Roflumilast over placebo may be of clinical relevance.

Following the analysis of literature data, SC members' opinion and for feasibility reasons the total number of enrolled Subjects has been capped at 150 in total.

The literature gives some guidance on expected drop-out rates in such a trial:

Citation	Patients screened	Randomized	Discontinued trial	Completed trial (had 2 bronchoscopies)
Bourbeau et al. 2007 [26]	62	60	9	51
Lapperre et al. 2009 [11]		114		90
Gamble et al. 2003 [21]	77	59	6	53
Hattotuwa et al. 2002(b) [27]		37		31
Barnes et al. 2006 [14]	162	140		114

The table above indicates that drop-out rates (expressed as a percentage of enrolled Subjects) may be as high as 30%. To have a conservative estimate a 30% drop-out rate is assumed in this trial. Thus, the trial may end up with 105 Subjects having two bronchoscopies.

The subsequent table below contains some example calculations for sample size. They are for the primary variable (subepithelial CD8+ cell count/mm²). Analysis by a Poisson regression model with dispersion parameter is assumed. Sample size was calculated according to formula (4.3) of Yee, 1998 [28]. Further assumptions were the following: 1:1 randomization, two-sided alpha = 0.05, power = 0.90, 0.85, 0.80, event rate on Roflumilast = 200 cells/mm², event rate on placebo 285 cells/mm². Such a reduction of event rates would correspond to an improvement of ca. 30% on Roflumilast (placebo event rate corresponds to 100%). Given the uncertainty in the assumptions around the mean area examined and the counts per mm², Takeda may conduct a blinded pooled assessment of these quantities and revise the sample size to ensure the study remains adequately powered.

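### Weight and BMI change, a known roflumilast harm, is modelled only by ANCOVA with LOCF, which mixes exposure times and probably dilutes the on-treatment week-16 difference

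*Protocol*

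**What the plan says.** Protocol section 13.1.5.3 says that weight and BMI change "will be analysed using an ANCOVA model including LOCF". The outcome is fixed there too: "The dependent variable will be the change from randomization (V2) to the last scheduled post-randomization visit up to visit V6". The covariates are treatment, baseline value and LABA pre-treatment. Descriptive statistics "will be provided for all scheduled visits (absolute values as well as changes from baseline) by treatment", and a subject listing is added. Further detail is left to the SAP, but the model and the imputation rule are already set.

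Other sections bear on this choice:

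- Section 9.1.4: "Body weight measurements will be performed at each visit from V0 to V7".
- Section 4.2 counts weight decrease among the events associated with roflumilast and says the pivotal studies "showed a larger mean weight loss in Roflumilast-treated patients compared to placebo-treated patients which was however reversible upon Roflumilast withdrawal".
- Section 13.3: "To have a conservative estimate a 30% drop-out rate is assumed in this trial".
- Section 9.3.5 requires the V6 assessments, apart from the bronchoscopy, for a subject who stops after V3. Section 7.8 and the notes to Appendix A extend them, where possible, to anyone who stops early. Weight is one of them.
- Section 13.1.3.3 uses a similar rule for the sputum and serum markers: change from baseline "to last available measurement during double-blind treatment".

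**The concern.** LOCF puts weight changes from different lengths of exposure into one outcome. A subject last weighed at week 2 or week 6 enters the model as if that change had been seen at week 16. The standard error makes no allowance for the value being imputed. If loss on roflumilast builds up over time, the carried values are smaller than the week-16 changes they stand for, and the treatment difference shrinks towards zero.

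This matters because the outcome is a recognised harm, the protocol allows for sizeable drop-out, and the LOCF result is the only adjusted treatment difference planned for weight. The plan does not say whether it means to estimate the effect while on treatment or the weight at week 16 whether or not treatment was stopped. LOCF estimates neither cleanly.

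**Working it through.** **The plan's own figure.** 150 × (1 − 0.30) = 105 completers, as in section 13.3. That leaves 45 subjects who stop early.

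**Drop-out range.** In the drop-out table of section 13.3, losses among randomized subjects are 9/60 = 15%, 24/114 = 21%, 6/59 = 10%, 6/37 = 16% and 26/140 = 19%. About 30% appears only when completers are set against screened subjects: (162 − 114)/162 = 29.6% and (77 − 53)/77 = 31.2%. The third such pair gives (62 − 51)/62 = 17.7%. So 30% is a conservative upper figure and 10 to 21% is the range among randomized subjects.

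**Set-up (assumptions, since the protocol gives no weight effect or time course).** The on-treatment difference at week 16 is set to 1. The placebo change is flat, loss on roflumilast is linear in time, drop-out times are uniform over 0 to 16 weeks, and drop-outs lose weight at the same rate as completers. V3 is placed at week 2; V4, V5 and V6 are at weeks 6, 14 and 16. With drop-out d and mean share s reached at the carried value, LOCF shows (1 − d) + d·s.

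**Carrying the last scheduled visit.**

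| Stops in weeks | Probability | Carried from week | Share of effect |
|---|---|---|---|
| 0–2 | 0.125 | none | – |
| 2–6 | 0.25 | 2 | 0.125 |
| 6–14 | 0.50 | 6 | 0.375 |
| 14–16 | 0.125 | 14 | 0.875 |

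The sum of probability × share is 0.031 + 0.188 + 0.109 = 0.328. Counting the first row as zero change gives 0.70 + 0.30 × 0.328 = 0.798. Section 13.1.5.3 requires a post-randomization visit, however, so those subjects have nothing to carry. Without them: 0.798 / (1 − 0.30 × 0.125) = 0.798 / 0.9625 = **0.83**.

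**Carrying the early-termination weight.** The mean share is 0.5, so 0.70 + 0.30 × 0.5 = **0.85**.

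**At 10 to 21% drop-out, early-termination weight carried.** 1 − 0.5 × 0.10 = **0.95** and 1 − 0.5 × 0.21 = 0.895, about **0.90**.

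**How far the assumptions matter (30% drop-out, early-termination weight carried).**

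- Loss complete by week 6: s = (6 × 0.5 + 10 × 1)/16 = 0.8125, so 0.70 + 0.30 × 0.8125 = 0.94.
- Drop-outs losing twice as fast: LOCF gives 0.70 + 0.30 × 2 × 0.5 = 1.00 with linear loss and 0.70 + 0.30 × 2 × 0.8125 = 1.19 with the plateau. The on-treatment target is then 0.70 + 0.30 × 2 = 1.30. LOCF is still below the target, but at or above the completers' 1.00.
- Target is week-16 weight regardless of stopping, with full reversal after stopping: the target is 0.70. LOCF at 0.85 to 0.94 overstates it by 0.85/0.70 − 1 = 21% to 0.944/0.70 − 1 = 35%.

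**The case against.** A reader might infer that LOCF simply understates the harm and that the bias runs in the drug's favour. The documents do not support that. They give no time course, no reasons for drop-out and no stated target. Section 4.2 says the loss reverses on withdrawal, so LOCF can overstate actual week-16 weight in those who stopped. Subjects who lose most may also be the ones who stop, so carried losses need not be small. This objection stands: dilution is expected for an on-treatment target with progressive loss, and neither its sign nor its size is established beyond that.

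It can also be said that the damage is limited. The early-termination weight brings the carried value closer to the time of stopping, 30% is a deliberately high drop-out figure, and missing the second bronchoscopy is not the same as missing a weight. These points also stand and are built into the range above. Whether the early-termination weight counts as the last scheduled visit may be settled in the SAP.

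Finally, weight is a descriptive safety outcome with no confirmatory test, by-visit summaries are planned, and weight-decrease adverse events are tabulated separately. This softens the consequence but does not remove it. The by-visit summaries give no adjusted difference, so the LOCF estimate remains the headline.

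**Conclusion.** The point holds in a limited form. The protocol fixes a weak method for a named harm although data for a better one are already scheduled. LOCF mixes exposure times, treats carried values as observed, and is likely, not certain, to dilute the on-treatment week-16 difference. Under linear loss and uniform drop-out the dilution is about 15 to 17% at 30% drop-out. It is about 5 to 10% at the drop-out seen among randomized subjects in the protocol's table, if the early-termination weight is carried. A faster plateau makes it smaller, and a target that ignores stopping can reverse its direction.

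The on-treatment target suits the schedule better. V7 is reserved for subjects who completed and had the final biopsy (section 9.3.6), so no weight is scheduled after the termination visit, and week-16 weight after stopping would be largely unobserved.

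For the sputum and serum markers, the last-available rule mixes weeks 6 and 14 in the same way. A reader might extend the argument about bias favouring the drug to them. It does not carry over, because diluting a benefit works against the drug. No size is claimed for those markers.

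**What to change.** In section 13.1.5.3:

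- State that the target is the on-treatment week-16 difference.
- Make the main analysis of weight and BMI change a mixed model for repeated measures on V3, V4, V5 and V6, with treatment, visit, treatment by visit, baseline by visit and LABA stratum. Report the V6 contrast as the main result.
- Assign early-termination weights to the nearest scheduled visit.
- Keep ANCOVA with LOCF as a sensitivity analysis.

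The same model may be used for the sputum and serum markers at V4 and V5.

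The cost is a change of wording and a little programming, since all the data are already collected. The downside is reliance on a missing-at-random assumption. The retained LOCF analysis gives a comparison but does not test that assumption.

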13.2 Interim Analysis and Criteria for Early Termination

No interim analysis is planned.

13.3 Determination of Sample Size

Based on the extensive literature search/review and experimental data provided by the Steering Committee (SC) members the team concludes that significant differences exist between reports published by various groups, which may be attributable to different patient populations, bronchoscopy/tissue harvesting/processing methods and statistical methods employed (see attached table below).

Additionally based on SC members' opinion a universally recognized level of clinical relevance regarding the first primary variable (sub-mucosa CD8+ cells) has not yet been agreed upon within the scientific community of chest physicians and pathologists. But it has been indicated by SC members that a 30% improvement on Roflumilast over placebo may be of clinical relevance.

Following the analysis of literature data, SC members' opinion and for feasibility reasons the total number of enrolled Subjects has been capped at 150 in total.

The literature gives some guidance on expected drop-out rates in such a trial:

Citation	Patients screened	Randomized	Discontinued trial	Completed trial (had 2 bronchoscopies)
Bourbeau et al. 2007 [26]	62	60	9	51
Lapperre et al. 2009 [11]		114		90
Gamble et al. 2003 [21]	77	59	6	53
Hattotuwa et al. 2002(b) [27]		37		31
Barnes et al. 2006 [14]	162	140		114

The table above indicates that drop-out rates (expressed as a percentage of enrolled Subjects) may be as high as 30%. To have a conservative estimate a 30% drop-out rate is assumed in this trial. Thus, the trial may end up with 105 Subjects having two bronchoscopies.

The subsequent table below contains some example calculations for sample size. They are for the primary variable (subepithelial CD8+ cell count/mm²). Analysis by a Poisson regression model with dispersion parameter is assumed. Sample size was calculated according to formula (4.3) of Yee, 1998 [28]. Further assumptions were the following: 1:1 randomization, two-sided alpha = 0.05, power = 0.90, 0.85, 0.80, event rate on Roflumilast = 200 cells/mm², event rate on placebo 285 cells/mm². Such a reduction of event rates would correspond to an improvement of ca. 30% on Roflumilast (placebo event rate corresponds to 100%). Given the uncertainty in the assumptions around the mean area examined and the counts per mm², Takeda may conduct a blinded pooled assessment of these quantities and revise the sample size to ensure the study remains adequately powered.

Total number of evaluable Subjects needed by mean tissue area and variability of measurements as expressed by dispersion parameter^{*)}.

Power	Mean area examined	Dispersion parameter			
		20	25	60	100
90%	0.3 mm ²	96	120	286	476
90%	0.4 mm ²	72	90	214	358
85%	0.3 mm ²	82	102	244	408
85%	0.4 mm ²	62	78	184	306
80%	0.3 mm ²	72	90	214	356
80%	0.4 mm ²	54	68	160	268

^{*)} Variance = dispersion parameter x Poisson expectation.

Thus, with a dispersion of 25 and a tissue area of at least 0.3 mm² and further assumptions as above, the trial would have a high power (ca. 90%) to detect treatment differences.

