2.0 STUDY SUMMARY

Name of Sponsor(s): Takeda Development Centre Europe Ltd.		Compound: Roflumilast	
Title of Protocol: A 16-week, randomized, placebo-controlled, double blind, and parallel group trial to assess the anti-inflammatory effects of Roflumilast in chronic obstructive pulmonary disease The ROBERT study		IND No.: Not Applicable	EudraCT No.: 2011-000582-13
Study Number: RO-2455-402-RD		Phase: III Clinical Exploratory	
Study Design: This is a phase III, randomized, placebo-controlled, double blind, and parallel group trial to assess the anti-inflammatory effects of Roflumilast in chronic obstructive pulmonary disease. The duration is 24 weeks maximum, and consists of the following periods: 
 • Single-blind placebo run-in period (6 weeks) with visits scheduled at weeks: -6 (V0), -2 (V1) and 0 (V2, randomization visit). • Double-blind treatment period (16 weeks) with visits scheduled at 6, 14, and 16 weeks of treatment (V4-V6). An additional visit V3 will have to be performed within two weeks after bronchoscopy/bronchial biopsy purely as a safety visit. The exact timing of this safety visit will be determined by the Investigator. • Safety follow-up. All adverse events (AEs) will be followed up to 30 days after the double-blind treatment period has been completed. An additional safety visit V7 will be scheduled within 2 weeks after the second bronchoscopy. The exact timing of the safety visit will be determined by the Investigator. 			
Primary Objectives: 
 • To investigate the effect of Roflumilast 500 µg tablets once daily versus placebo on inflammatory cells (CD8+) in bronchial biopsy tissue specimens. 			
Secondary Objectives: 
 • To investigate inflammatory cells and parameters in bronchial biopsy tissue, sputum and blood serum. • Safety status will be assessed by vital signs, physical examination (including electrocardiogram [ECG]), clinical laboratory tests, and monitoring of adverse events. 			
Subject Population: Patients with COPD (GOLD stage II-III, in Germany stage II only)			
Number of Subjects: A total of 150 Subjects is to be randomized (1:1) into two treatment arms (Roflumilast 500 µg or placebo).		Number of Sites: Estimated total: Approximately 25 sites in Europe.	

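### The stated power of about 90% does not follow from the plan's own figures: 105 evaluable subjects give about 86% at dispersion 25 and 0.3 mm², and 90% needs 120.

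*Protocol*

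**What the plan says.** Section 13.3 of the protocol builds the sample size in four steps.

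- **Cap.** Enrolled subjects are capped at 150. The synopsis (section 2.0) repeats this cap and also says: "A total of 150 Subjects is to be randomized (1:1) into two treatment arms".
- **Drop-out.** After a table of five published biopsy trials, the text reads: "The table above indicates that drop-out rates (expressed as a percentage of enrolled Subjects) may be as high as 30" per cent. It adopts 30% as a conservative value and concludes: "Thus, the trial may end up with 105 Subjects having two bronchoscopies".
- **Table.** A table gives the total number of evaluable subjects by power, mean area examined and dispersion. Its assumptions are "1:1 randomization, two-sided alpha = 0.05, power = 0.90, 0.85, 0.80", "event rate on Roflumilast = 200 cells/mm²" and 285 cells/mm² on placebo. At dispersion 25 and 0.3 mm² it lists 120 subjects for 90% power, 102 for 85% and 90 for 80%.
- **Conclusion.** With dispersion 25, a tissue area of at least 0.3 mm² and the other assumptions already listed, "the trial would have a high power (ca. 90%) to detect treatment differences". The synopsis repeats this sentence under its sample size justification, after the figure of 105.

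**The concern.** The table is in evaluable subjects, so it should be entered with the number left after drop-out. That number is 105, which lies just above the 85% entry (102) and 15 short of the 90% entry (120). The concluding sentence therefore appears to use the 30% loss for the head count and ignore it for the power.

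There is a second problem with the 30% itself. It is described as a share of enrolled subjects and applied to 150. In the cited trials a loss near 30% arises only when completers are divided by patients screened. Section 13.1.1.1 counts subjects withdrawn before randomization as enrolled, so enrolled and randomized are not the same group in this protocol.

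At stake is the power statement for the primary endpoint. It appears twice, and it supports the size of a trial that asks each subject to undergo two research bronchoscopies.

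**Working it through.** **Inputs, all from section 13.3.** Two-sided alpha 0.05; 1:1 allocation; rates 200 and 285 cells/mm²; variance equal to dispersion times the Poisson expectation; dispersion φ = 25; area t = 0.3 mm²; 150 subjects; 30% drop-out.

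**1. Reproduce the table.** For a Wald test on the log rate ratio with over-dispersion,

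n per arm = (z₀.₉₇₅ + z_power)² × (φ/t) × (1/200 + 1/285) / [ln(200/285)]².

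Here 1/200 + 1/285 = 0.008509, ln(200/285) = −0.3542, its square is 0.12544, and φ/t = 83.33.

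| Power | (z₀.₉₇₅ + z_power)² | n per arm | Rounded up | Total | Protocol table |
|---|---|---|---|---|---|
| 90% | 10.507 | 59.40 | 60 | 120 | 120 |
| 85% | 8.978 | 50.75 | 51 | 102 | 102 |
| 80% | 7.849 | 44.37 | 45 | 90 | 90 |

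The same formula reproduces all 24 entries of the table exactly, so the table is sound.

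**2. Power at the plan's evaluable number.** 150 × 0.70 = 105, or 52.5 per arm.

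- Standard error of the log rate ratio = √(83.33 × 0.008509 / 52.5) = 0.1162.
- 0.3542 / 0.1162 = 3.048.
- Power = Φ(3.048 − 1.960) = Φ(1.088) = 0.862.

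Four other versions of the test (null-variance Wald, rate difference, square-root scale, likelihood-ratio non-centrality) give at most 86.8% at 105. The choice of formula does not recover 90%.

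**3. What 90% would take.**

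- With 0.3 mm² and dispersion 25: 120 evaluable. At 30% loss that is 120 / 0.70 = 171.4, so 172 randomized against a cap of 150.
- With 105 evaluable and dispersion 25: a mean area of about 0.34 mm².
- With 105 evaluable and 0.3 mm²: a dispersion of about 22.

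**4. The drop-out table.** Studies are listed in the protocol's order.

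| Study | Completed / randomized | Lost | Completed / screened | Lost |
|---|---|---|---|---|
| 1 | 51/60 | 15.0% | 51/62 | 17.7% |
| 2 | 90/114 | 21.1% | not given | – |
| 3 | 53/59 | 10.2% | 53/77 | 31.2% |
| 4 | 31/37 | 16.2% | not given | – |
| 5 | 114/140 | 18.6% | 114/162 | 29.6% |
| Pooled | 339/410 | 17.3% | | |

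No study lost more than 21.1% after randomization.

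**5. Power if 150 are randomized and loss follows these studies** (dispersion 25, 0.3 mm², formula of step 2).

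| Loss | Evaluable | Power |
|---|---|---|
| 21.1% | 150 × 90/114 = 118 | 89.8% |
| 17.3% | 150 × 339/410 = 124 | 91.2% |
| 10.2% | 150 × 53/59 = 135 | 93.3% |

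**The case against.** The strongest reply is that the sentence is hedged. It says approximately 90% and gives 0.3 mm² as a minimum, and 105 is introduced as a conservative figure. At 105 evaluable and dispersion 25, power is about 91% at 0.35 mm² and 94% at 0.4 mm². If loss resembles the cited trials, power is close to or above 90% even at 0.3 mm². The sponsor may also reassess area and counts on blinded pooled data and revise the sample size. The gap is about 4 points, while at 105 evaluable and 0.3 mm² a change in dispersion from 25 to 20 alone moves power from 86% to 93%.

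Part of this stands. The shortfall is modest, and the trial may well reach 90%. The use of 150 as the number randomized is also recoverable: section 7.8 recruits to a planned number randomized, and section 8.2 treats 150 as the number assigned to treatment.

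It does not rescue the sentence. A claim made for an area of at least 0.3 mm² has to hold at 0.3 mm². The protocol does not support relying on more: section 9.1.15.2 uses 0.3 mm² as a sample-quality threshold, and the Biopsy Laboratory Manual (Appendix G, 2.4) accepts 0.1 mm² per patient. If 30% is the conservative case, the power quoted with it should be the power in that case. The blinded reassessment is optional and does not cover drop-out. The table itself treats 85% and 90% as separate targets, and 86.2% is nearer the first.

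**Conclusion.** The concern holds. On the protocol's own assumptions (285 against 200 cells/mm², two-sided 5%, dispersion 25, mean area 0.3 mm², 105 evaluable subjects) power is 86.2%, 3.8 points below the stated figure. The type II error is about 14% instead of 10%. The table is correct; the sentence drawn from it is not.

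The 30% drop-out matches the cited literature only as a share of patients screened. Applied to 150 randomized subjects, it understates the evaluable number that the same literature implies (118 to 135, about 124 pooled). The two faults pull in opposite directions: correcting only the power gives about 86%, and correcting the loss rate as well gives about 91%. The protocol has to choose one basis and quote the power that belongs to it.

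**What to change.** Change section 13.3 and the synopsis together.

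1. If 30% loss and 105 evaluable are kept, replace the power statement by about 86% with 105 evaluable subjects, at dispersion 25 and 0.3 mm².
2. If loss after randomization is the intended assumption, replace 30% and 105 by a rate taken from the completed/randomized columns, with its evaluable number and power. At the pooled 17.3% these are about 124 evaluable and about 91%; across the five studies they are 118 to 135 evaluable and about 90% to 93%.
3. In either case, say that 150 is the number randomized, use that word in place of enrolled throughout the sample-size text, and name the denominator of the drop-out rate.

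The cost is wording in two places. Under option 1 the stated power becomes slightly less favourable. Neither option needs extra patients or any change to the test, the endpoint or the recruitment target.
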